9.4.1 Study Procedures

9.4.1.1 Informed consent process

Eligible subjects can only be included in the study after they have provided the written informed consent. Study procedures will be explained to the subjects and their written informed consent must be obtained before starting any procedure required by the protocol. All subjects will be also informed on the required restrictions detailed in § 8.3.4.

The process of obtaining the informed consent shall be documented in the subject source documents.

9.4.1.2 Screening (within 4 weeks prior to 1st PK study session, including genotyping)

At Screening, each subject will attend the study site in fasting condition (for at least 10 h) for the following procedures:

- Collection of demographic data.
- Recording of medical history, including prior and concomitant medications.
- Physical examination, including height and weight to calculate BMI.
- Recording of vital signs including Frontal Body Temperature, supine, and SBP, DBP, PR, RR and 12-lead ECG, to be measured after at least 10-minute rest. In addition, SBP and DBP are to be measured after standing for 2-5 minutes.
- Blood sampling for:
 - Genotyping for CYP2D6 mutational status (see § 9.4.2)
 - Haematology and biochemistry safety laboratory tests.
 - Serology for HIV I and II, HBV and HCV.
 - Pregnancy test (β -HCG in serum) in female subjects (if applicable)
- Urine collection for:
 - Drugs of abuse screening test for cocaine and metabolites (COC 300), Amphetamine (AMP 500), Methamphetamine (MET 500), Marijuana (including Cannabinoids THC) (THC 50), Opiates (including Heroin Morphine and metabolites) (MOP 300), Methylenedioxymethamphetamine Ecstasy (MDMA 500), Methadone (MTD 300);
 - o Cotinine;
 - o Urinalysis.
- Alcohol salivary test.
- Recording of any Clinical Event, not associated to any drug intake (Clinical Event; § 9.5.2.3) and/or of any Adverse Event (§ 9.5.3.1), associated to any drug intake that occurs for the first time or worsens after the signature of the Informed Consent and prior to Investigational Medicinal Product (IMP) administration, if any.
- Check of inclusion/exclusion criteria.

Subjects who do not meet ALL inclusion criteria or meet ANY of the exclusion criteria listed in § 8.3.2 and § 8.3.3, respectively, and those with any clinically significant abnormality (including laboratory values, vital signs and 12-lead ECG) will not be considered as eligible to be randomized to study treatments and will not continue the study.

Once a subject's eligibility has been confirmed, the dates for the three PK study sessions shall be scheduled and the subject shall be instructed to attend the study site i n the evening of the day prior to each PK study session and to adhere to the study restrictions as reported in § 8.3.4.

NOTE 1: re-screening to evaluate subject's eligibility is allowed provided that the subject has not already been randomized.

NOTE 2: Genetic evaluation of CYP2D6 activity is not required if previous results are made available to the Investigator.

9.4.1.3 Pharmacokinetic Study Sessions

Subjects will be resident at the study site from the evening of the day prior to each PK study session until the 72-h post dosing, after PK sampling and study procedures have been completed.

Each study session should be separated by a minimum of 14-day wash-out period between each IMP intake.

Subjects must abstain from extraneous exercise during residence at the study site.

Study procedures to be applied to the PK study sessions are described below.

Pre-dosing procedures will be performed as follows:

NOTE: pre-dosing procedures can be performed on Day - 1, i.e. the day before dosing, the only exception being the 'Baseline' procedures listed below)

- Recording of any Clinical Event, not associated to any drug intake (Clinical Event; § 9.5.2.3 NOTE) and/or of any Adverse Event (§ 9.5.2.3), associated to any drug intake that occurs for the first time or worsens after the signature of the Informed Consent and prior to IMP administration, if any, and/or any medication change since the screening visit/previous study session, if any.
- Check of adherence to the study restrictions.
- Physical examination.
- Urine collection for:
 - Pregnancy test (β -HCG in urine) in female of childbearing potential.
 - Drugs of abuse screening test for cocaine and metabolites (COC 300), Amphetamine (AMP 500), Methamphetamine (MET 500), Marijuana (including Cannabinoids THC) (THC 50), Opiates (including Heroin Morphine and metabolites) (MOP 300), Methylenedioxymethamphetamine Ecstasy (MDMA 500), Methadone (MTD 300).
 - Cotinine test.
- Alcohol salivary test.
- Re-check of inclusion/exclusion criteria.
- Randomization (applicable to 1st PK session only).
- Baseline recording (T+0'), within 1 hour from dosing of vital signs including Frontal Body Temperature, supine SBP and DBP, PR, RR and 12-lead ECG, to be measured after at least 10-minute rest.
- Baseline blood sample (T+0') of 8 mL for PK plasma assay within 30 minutes from dosing.

Dosing will start after baseline (prior to dosing) procedures are completed, with one of two oral treatments to be administered as per randomization sequence:

- NEB/RAM 5/10 mg FDC;
- NEB 5 mg + RAM 10 mg EC;

All treatments shall be orally taken in the morning, at $8:00 \pm 1$ h, in fasting condition with 240 mL of still water.

NOTE: The two tablets of the extemporaneous combination should be taken almost simultaneously, i.e. one immediately after the other, with Nebivolol to be taken first, followed by Ramipril tablet. Intake time will be recorded for each tablet.

Subjects will be required to fast for at least 10 h overnight prior to each morning dose. The fast will be broken approximately 4 h after dosing with a light standard lunch. Subjects will not be allowed to drink any water 1 h before and 1 h after the dosing, with the exception of water foreseen for treatment administration.

In order to maintain adequate hydration, the subjects will be encouraged to drink at least 180 mL of still mineral water every 2 h for 5 h post-dose, starting at 1 h post-dose.

After dosing, the following procedures will be performed:

• Recording at T+1.5 h, T+6 h, T+ 12h and T+ 24h of vital signs including supine SBP and DBP, PR, and 12-lead ECG, to be measured after at least 10-minute rest (when overlapping, recording to be done within 30 min before PK sampling)

Blood sampling for PK analysis (8 mL: 5 mL for Nebivolol and 3 mL for Ramipril and Ramiprilat, each), for plasma assay at the following predefined time points:

Nebivolol and Ramiprilat PK samples: T+5', T+15', T+30', T+45', T+1h, T+1.25h, T+1.5h, T+2h, T+2.5h, T+3h; T+3.5h, T+4h, T+6h, T+8h, T+10h, T+12h, T+24h, T+48h and T+72h post dose.

Ramipril PK samples: T+5', T+15', T+30', T+45', T+1h, T+1.25h, T+1.5h, T+2h, T+2.5h, T+3h; T+3.5h, T+4h, T+6h, T+8h, T+10h, T+12h, T+24h, post dose.

A time window for blood sample collection is allowed as follows:

 ± 2 minutes for blood sampling from T+15' to T+4h;

 \pm 5 minutes for blood sampling from T+5h to T+24h;

 \pm 30 minutes for blood sampling from T+48h to T+72h.

Before discharge from the Unit,

Recording of any AE that occurred during all the experimental phase and of all the concomitant medications taken, if any.

9.4.1.4 End of Study Visit (10-12 days after last treatment administration)

The following examinations and tests will be performed during this visit:

- Recording of vital signs including Frontal Body Temperature and supine SBP and DBP, PR, RR and 12-lead ECG, to be measured after at least 10-minute rest.
- Physical examination
- Blood sampling for haematology and biochemistry.
- Urine collection for:
 - Pregnancy test (β -HCG in urine) in female subjects (if applicable),
 - o Urinalysis.
- Recording of AEs that occurred between the last study session and the End of Study visit and concomitant medications taken, if any.

The total amount of blood that will be collected for safety and PK assessment during the whole study duration is approximately 506 mL (see Table 2).

This volume only slightly exceeds a normal blood donation and is collected in a time period of at least 2 months.

Table 2. Total blood volume withdrawn relative to Screening, 3 PK sessions and End of Study	
Visit.	

Sample type	Volume (mL)	Number	Sub-Total (mL)
РК	8	60	480
Biochemistry	8.5	2	17
Haematology	4	2	8
HIV-1, HIV-2, HBV, HCV*	NA	NA	NA
CYP2D6	1	1	1
			TOTAL=506 mL

*Volume included with Haematology volume (also Volume for pregnancy test in serum at screening is included)

Final Version 1.0, 28th March 2023

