Individual concentrations deemed to be anomalous will not be excluded from the PK analysis and mean profiles; anyway, such anomalous values will be identified in the relevant tables of study report. Anomalous values are those that are inconsistent with known or expected PK behaviour of the drug, and are not defined in a statistical outlier sense. Exclusion of data can be accepted only under the following circumstances:

- Drop out/withdrawn subjects
- A subject with lack of any measurable concentrations or only very low plasma concentrations for reference formulation. A subject is considered to have very low plasma concentrations if its AUC is less than 5% of reference medicinal product

geometric mean (GM) AUC (which should be calculated without inclusion of data from the outlying subject).

- Subjects with non-zero baseline concentrations > 5% of C_{max} . Such data will be excluded from bioequivalence calculation. The above can be due to subjects' noncompliance and/or to an insufficient wash-out period.
- A subject may be excluded from the PK population if there are any important protocol deviations or adverse events (AEs) that may impact PK. Additional details on exclusion criteria will be provided in the SAP.

Clear justification will be provided in the report for exclusion of any data.

9.4.2.2 Sampling and handling of pharmacokinetic blood samples

Blood samples for PK plasma assay of Nebivolol, Ramipril and Ramiprilat analytes (8 mL: 5 mL for nebivolol and 3 mL for Ramipril and Ramiprilat, at each time-point) are required from T+0 (baseline) up to 72 h post dose as reported under § 9.4.1.2.

Actual sampling times for each subject will be recorded in the individual electronic case report forms (eCRFs). The actual sampling times should not exceed the recommended tolerance ranges presented in the section above. Any deviation outside the recommended ranges will be verified through automatic queries and, if confirmed, will be reported as protocol deviation, although it will not automatically lead to the exclusion of the concerned subjects from the PK population.

The total amount of blood collected from each subject for PK assessment for the overall study sessions is up to 480 mL.

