Blood samples for PK analysis will be collected using an indwelling catheter with switch valve. The cannula will be rinsed, after each sampling, with about 1 mL of sterile saline solution. The first 1 mL of blood will be discarded at each collection time from the cannula.

The remaining blood volume will be collected from the catheter and transferred with a syringe into heparinised tubes (Li-heparin).

The samples will be stored on ice for a maximum of 30 min. Then they were centrifuged at 4° C for 10 min at 1900 g to obtain plasma. Each plasma sample was immediately divided into 4 aliquots in pre-labelled polypropylene tubes:

- P1 and P2 (for Nebivolol) with 0.8 mL each
- P3 and P4 (for Ramipril and Ramiprilat) with 0.5 mL each

If the plasma obtained is insufficient, transfer the required volume in aliquots P1 and P3 and the remaining volume in aliquots P2 and P4.

All the aliquots were stored frozen, at temperatures -80°C (\pm 15°C), within 30 min from the end of centrifugation.

9.4.2.3 Samples labelling

Study day

Each sample tube will be clearly and unequivocally identified with a label resistant to the storage temperature and reporting: Study code Study CRO-PK-23-364 - Sponsor code NEB-RAM-01 Subject number Tube identification P1/P2/P3/P4 Period

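### Table 2's 506 mL omits the 1 mL discarded at each of 60 PK draws (up to 566 mL withdrawn), and the two-month minimum collection period is not guaranteed

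*Protocol*

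**What the plan says.** The table in Protocol 9.4.1.4 is headed "Total blood volume withdrawn relative to Screening, 3 PK sessions and End of Study". It lists PK samples (8 mL, 60 draws, 480 mL), biochemistry (17 mL), haematology (8 mL) and CYP2D6 (1 mL), and totals 506 mL. The text beside it concludes: "This volume only slightly exceeds a normal blood donation and is collected in a time period of at least 2 months".

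The subsection on sampling and handling of PK blood samples (numbered 9.4.2.2, inside section 9.4.3) assigns the sample volume as "8 mL: 5 mL for nebivolol and 3 mL for Ramipril and Ramiprilat, at each time-point" and states: "The total amount of blood collected from each subject for PK assessment for the overall study sessions is up to 480 mL". The same subsection says the cannula is rinsed with about 1 mL of saline after each sample, and then: "The first 1 mL of blood will be discarded at each collection time from the cannula". What follows the discard goes into the heparinised tubes.

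On timing, 9.4.1.3 sets a minimum of 14 days between doses. Section 8.1 places the last PK sample at 72 hours and the End of Study Visit 10 to 12 days after the last dose, and expects an individual duration of about 10 weeks. The flow-chart notes in 2.2 give screening a maximum of 4 weeks and no minimum.

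Section 6.2 judges the total volume acceptable in view of the healthy population and the study duration.

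**The concern.** Section 6.2 rests its judgement on blood volume partly on how much is taken and over how long. Both inputs appear to err in the reassuring direction. A table that claims to show everything withdrawn has no line for blood that the procedure orders to be drawn and thrown away. The period is worded as a floor, but the schedule fixes only the shortest wash-out and the longest screening window, so it sets no such floor.

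What is at stake is the accuracy of the burden and safety information that the ethics committee reviews. The sample size, error rate, PK endpoints and bioequivalence decision are not affected.

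**Working it through.** **Inputs.** Time points per session (9.4.1.3): 1 baseline + 19 post-dose. Sessions: 3. Sample: 5 + 3 = 8 mL. Discard: 1 mL per draw (9.4.2.2). Other blood (Table 2): 17 + 8 + 1 = 26 mL.

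**Step 1: reproduce the plan's figure.**
- Draws = 3 × (1 + 19) = 60
- PK = 60 × 8 = 480 mL
- Total = 480 + 17 + 8 + 1 = 506 mL

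This matches Table 2 exactly, so the table contains no discard term.

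**Step 2: add the discard.** The whole 8 mL is assigned to the two assays, so the discard comes on top of it. The documents do not say how much of each discarded millilitre is rinse saline, so the blood share is varied from none to all:

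| Blood in each 1 mL discard | Added volume | PK sessions | Total | Stated 506 mL falls short by |
|---|---|---|---|---|
| 0 mL (all saline) | 0 | 480 mL | 506 mL | 0% |
| 0.5 mL (illustrative assumption) | 30 mL | 510 mL | 536 mL | 30/536 = 5.6% |
| 1 mL (as the text is worded) | 60 mL | 540 mL | 566 mL | 60/566 = 10.6% |

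**Step 3: time.**
- Shortest span of PK sampling: 14 + 14 + 3 = 31 days from first dose to the last 72-hour sample.
- First dose to End of Study at minimum wash-outs: 28 + 10 = 38 to 28 + 12 = 40 days.
- With the full 28-day screening window added: 28 + 38 = 66 to 28 + 40 = 68 days.
- Taking two months as 60 days (an assumption), minimum wash-outs reach it only if screening starts 60 − 40 = 20 to 60 − 38 = 22 days or more before the first dose.

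Only the 26 mL in the non-PK rows of Table 2 is taken outside the PK samples. So 480/506 = 94.9% of the stated volume can fall within the 31 days.

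**The case against.** **Wording.** The running text in 9.4.1.4 and 9.4.2.2 speaks of blood collected for assessment, and discarded blood is not collected for that purpose. On that reading 506 mL and 480 mL are correct for what they describe. This stands, and it narrows the error to the table heading, which speaks of blood withdrawn, and to the conclusions drawn from the table.

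**Saline.** The discard clears a line just rinsed with about 1 mL of saline, so part of it is plausibly not blood. This also stands. It makes 566 mL a ceiling, although the protocol itself calls the discard blood.

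**Discard inside the 8 mL.** This would preserve 506 mL, but it would leave 7 mL for tubes that are to receive 5 + 3 mL. It fits the text poorly.

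**Duration.** Section 8.1 expects about 10 weeks. The shortest case needs every wash-out at its minimum, and screening takes time because all results, including CYP2D6 sequencing where no earlier result exists, must be available before randomisation. So 31 days is the shortest span, not the typical one. An expectation is still not a minimum.

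**Stronger readings a reader might infer.**
- *The 8 mL draw is larger than needed.* The aliquots are "P1 and P2 (for Nebivolol) with 0.8 mL each" and "P3 and P4 (for Ramipril and Ramiprilat) with 0.5 mL each", or 1.6 + 1.0 = 2.6 mL of plasma, which is 32.5% of 8 mL. Whether less blood would do depends on a plasma yield that the documents do not give. The protocol foresees shortfalls ("If the plasma obtained is insufficient, transfer the required volume in aliquots P1 and P3"), so some reserve appears intended, and the second aliquots are the back-up for reanalysis. A smaller draw is not supported.
- *A 450 mL limit is breached.* Exclusion criterion 6 concerns blood lost before first dosing. It is an entry condition and not a cap on study sampling.
- *Subjects were told too low a figure.* The consent pages are not available, so this cannot be checked.

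**Conclusion.** The point holds as a correction of stated figures. Table 2 claims to show total blood withdrawn but omits the discard. The total is up to 566 mL, within a range of 506 to 566 mL set by the unknown saline share, so the stated figure is up to 10.6% below the true one. For the PK sessions alone, withdrawal is up to 540 mL. This rests on the discard being additional to the 8 mL, which is the natural reading because the 8 mL is fully allocated.

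The two-month period is a reasonable description of the expected course but not a minimum. At the shortest permitted intervals, PK blood is drawn within about 31 days and the End of Study Visit falls 38 to 40 days after the first dose.

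The documents give no volume for a normal blood donation, so the claim of a slight excess cannot be tested from them. It does, however, rest on a total that leaves out the discard. No serious harm to subjects is shown, and none is claimed here.

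**What to change.** 1. In Table 2, add a row for discarded blood (60 × up to 1 mL) and restate the total as up to 566 mL including discards.
2. In 9.4.2.2, keep 480 mL as the sampled PK volume and note that withdrawal in the PK sessions is up to 540 mL including discards.
3. In 9.4.1.4, replace the two-month minimum with: about 2 months; PK blood may be drawn within about 31 days at the minimum interval. Reconsider the blood-donation comparison against the corrected total.
4. In 6.2, base the acceptability statement on these figures.

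The cost is one table row and a few sentences. Sampling times, draw volume, aliquots, visits, endpoints and analysis stay as they are. If the sponsor intended the discard to come out of the 8 mL, the total of 506 mL can stay, but the 5 + 3 mL allocation must then be corrected.

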9.4.2 Sample collection for CYP2D6 analysis

In order to only include normal metabolizers for CYP2D6 based on the genotype, subjects will be assessed for their CYP2D6 mutational status. A blood sample collected during Screening will be used for this assessment. CYP2D6 will be analysed using next-generation sequencing (NGS). Each genetic testing result will include information on the identified genetic variants as well as metabolizer classification (poor, intermediate, extensive or ultra- rapid metabolizers) and clinical interpretation of the result.

9.4.3 Assessment of Pharmacokinetics

9.4.3.1 Calculation of pharmacokinetic parameters

Pharmacokinetic parameters for Nebivolol, Ramipril and Ramiprilat will be derived from individual measured concentrations by means of non-compartmental analysis (NCA) using PhoenixTM WinNonlin® software, version 8.3.5 or higher (Pharsight Corp., Mountain View, California).

The following PK parameters will be determined following partial replicated administration of Test and Reference formulations, as appropriate, by period, resulting in 2 PK profiles for EC, and one PK profile for FDC.

C _{max}	Maximum plasma concentration
t _{max}	Time to C _{max}
Clast	Last quantifiable plasma concentration observed
t _{last}	Time corresponding to Clast
λ_z	Apparent terminal elimination rate constant, estimated by log-linear regression analysis on plasma concentrations visually assessed to be on the terminal log-linear phase.
t _{1/2}	Plasma terminal half-life, calculated according to the following equation: $t_{1/2} = \frac{0.693}{\lambda_z}$
AUC _(0-t)	Area under the plasma concentration-time curve from time zero (baseline) to the time of the last quantifiable concentration, calculated by means of the linear-log trapezoidal method
AUC(0−∞)	Area under the plasma concentration-time curve from time zero to infinity, calculated according to the following equation: $AUC_{(0-\infty)} = AUC_{(0-t)} + \frac{C_{last}}{\lambda_z}$
AUC(0-72)	Area under the plasma concentration-time curve from time zero (baseline) to 72h post-dose
%AUC _{extrap}	The percentage of AUC $(_{0-\infty})$ obtained by extrapolation (%AUC _{extrap}) will be calculated as follows: $%AUC_{ex} = \frac{AUC_{(0-\infty)} - AUC_{(0-t)}}{AUC_{(0-\infty)}} \times 100$

Other PK parameters can be calculated, if considered appropriate and justified at the time of the PK analysis.

Actual PK sampling times will be used in the derivation of non-compartmental PK parameters. Nominal sampling times may be used as a replacement for unknown or missing actual times.

Concentration values below the Lower Limit of Quantification (LLOQ) will be set to zero. Concentrations reported as >LLOQ at time zero, when the subject has not previously been dosed, will be set to their real value.

Individual concentrations deemed to be anomalous will not be excluded from the PK analysis and mean profiles; anyway, such anomalous values will be identified in the relevant tables of study report. Anomalous values are those that are inconsistent with known or expected PK behaviour of the drug, and are not defined in a statistical outlier sense. Exclusion of data can be accepted only under the following circumstances:

- Drop out/withdrawn subjects
- A subject with lack of any measurable concentrations or only very low plasma concentrations for reference formulation. A subject is considered to have very low plasma concentrations if its AUC is less than 5% of reference medicinal product

geometric mean (GM) AUC (which should be calculated without inclusion of data from the outlying subject).

- Subjects with non-zero baseline concentrations > 5% of C_{max} . Such data will be excluded from bioequivalence calculation. The above can be due to subjects' noncompliance and/or to an insufficient wash-out period.
- A subject may be excluded from the PK population if there are any important protocol deviations or adverse events (AEs) that may impact PK. Additional details on exclusion criteria will be provided in the SAP.

Clear justification will be provided in the report for exclusion of any data.

9.4.2.2 Sampling and handling of pharmacokinetic blood samples

Blood samples for PK plasma assay of Nebivolol, Ramipril and Ramiprilat analytes (8 mL: 5 mL for nebivolol and 3 mL for Ramipril and Ramiprilat, at each time-point) are required from T+0 (baseline) up to 72 h post dose as reported under § 9.4.1.2.

Actual sampling times for each subject will be recorded in the individual electronic case report forms (eCRFs). The actual sampling times should not exceed the recommended tolerance ranges presented in the section above. Any deviation outside the recommended ranges will be verified through automatic queries and, if confirmed, will be reported as protocol deviation, although it will not automatically lead to the exclusion of the concerned subjects from the PK population.

The total amount of blood collected from each subject for PK assessment for the overall study sessions is up to 480 mL.

Blood samples for PK analysis will be collected using an indwelling catheter with switch valve. The cannula will be rinsed, after each sampling, with about 1 mL of sterile saline solution. The first 1 mL of blood will be discarded at each collection time from the cannula.

The remaining blood volume will be collected from the catheter and transferred with a syringe into heparinised tubes (Li-heparin).

The samples will be stored on ice for a maximum of 30 min. Then they were centrifuged at 4° C for 10 min at 1900 g to obtain plasma. Each plasma sample was immediately divided into 4 aliquots in pre-labelled polypropylene tubes:

- P1 and P2 (for Nebivolol) with 0.8 mL each
- P3 and P4 (for Ramipril and Ramiprilat) with 0.5 mL each

If the plasma obtained is insufficient, transfer the required volume in aliquots P1 and P3 and the remaining volume in aliquots P2 and P4.

All the aliquots were stored frozen, at temperatures -80°C (\pm 15°C), within 30 min from the end of centrifugation.

9.4.2.3 Samples labelling

Study day

Each sample tube will be clearly and unequivocally identified with a label resistant to the storage temperature and reporting: Study code Study CRO-PK-23-364 - Sponsor code NEB-RAM-01 Subject number Tube identification P1/P2/P3/P4 Period

